## 1. Abbreviations

ACA	Anterior Cerebral Artery
ACE	Angiotensin Converting Enzyme
ADA	American Diabetes Association
AE	Adverse Event
ALT	Alanine transaminase
ASL	Arterial Spin Labeling
AST	Aspartate aminotransferase
ARB	Angiotensin Receptor Blocker
BMI	Body Mass Index
BP	Blood Pressure
CBF	Cerebral blood flow
CEC	Clinical Events Adjudication Committee
CFDA	China Food and Drug Administration
CI	Confidence Interval
CRF	Case Report Form
CT	Computer Tomography
CTP	Computed Tomography Perfusion
DICOM	Digital Imaging and Communications in Medicine
DSA	Digital Subtraction Angiography
DSMB	Data Safety Monitoring Board
EoT	End of Trial
FAS	Full Analysis Set
HDL	High Density Lipoprotein
ICG	Indocyanine Green
IDL	Intermediate Density Lipoproteins
IEC	Independent Ethics Committee
IRB	Institutional Review Board
LDL	Low Density Lipoprotein
MCA	Middle Cerebral Artery

MI	Myocardial Infarction
MMD	Moyamoya Disease
MoCA	Cognitive Functional Outcome by the Montreal Cognitive Assessment
MR	Magnetic Resonance
mRS	Modified Rankin Scale
NIHSS	National Institute of Health Stroke Scale
SAE	Serious Adverse Event
SAP	Statistical Analysis Plan
STA	Superficial Temporal Artery
TIA	Transient Ischemic Attacks
UADE	Unanticipated Adverse Device Effect
VLDL	Very Low Density Lipoproteins

## 2. Protocol Synopsis

Title	Multimodal Neuronavigation Guiding Precision Bypass in Adult Ischemic Patients with Moyamoya Disease
Acronym	PBM
Objectives	To determine whether direct bypass surgery guided by multimodal neuronavigation is superior to empirical direct bypass procedure for preventing the primary endpoint (All strokes & death within 30 days post-surgery and ipsilateral hemorrhage afterwards) after cerebral revascularization surgery in ischemic MMD patients.
Study Design	
This will be an investigator-initiated and single center trial in which patients with ischemic symptoms (such as TIA, stroke) or asymptomatic MMD after symptom onset prior to enrollment that is caused by stenosis or occlusion in the terminal portion of the internal carotid artery and/or the initial portion of the anterior or middle cerebral arteries unilaterally or bilaterally and formation of abnormal collateral networks (moyamoya vessels) at the base of the brain will be randomized (1:1) to:
 
Direct bypass surgery guided by multimodal neuronavigation.
 
Combine local cerebral blood flow velocity and superficial perfusion assessed by Flow800 software that implements conventional ICG fluorescence angiography and deep perfusion assessed by multimodal MR (structure combined with perfusion sequence) to determine the recipient vessel.
 
OR
 
Empirical direct bypass surgery.

Primary endpoint	All strokes & death within 30 days post-surgery and ipsilateral hemorrhage afterwards
Secondary endpoint	
 
• All kinds of adverse events related to surgery within 30 days
 
• Infarctions on the contralateral side within 2 years of randomization
 
• Transient ischemic attack on the surgically treated side within 2 years of randomization
 

	
 
• The changes from baseline in CBF measured by ASL at 7 days, 3 months, 6 months, 12 months or end of trial
 
• The changes from baseline in modified Rankin Scale (mRS) at 7 days, 3 months, 6 months, 12 months or end of trial
 
• The changes from baseline in National Institute of Health Stroke Scale (NIHSS) at 7 days, 3 months, 6 months, 12 months or end of trial
 
• The changes from baseline in modified Barthel Scale at 7 days, 3 months, 6 months, 12 months or end of trial
 


Inclusion Criteria
	
 
• Independent in activity of daily living(The modified Rankin Scale 0-2)
 
• At least one month since the most recent ischemic stroke
 
• The neurological deficit must be stable for more than 6 weeks
 
• Digital subtraction angiography demonstrating progressive stenosis or occlusion in the terminal portion of the internal carotid artery and/or the initial portion of the anterior or middle cerebral arteries
 
• Digital subtraction angiography demonstrating formation of abnormal collateral networks(moyamoya vessels) at the base of the brain,mainly in the region of thalamus and basal ganglia
 
• Digital subtraction angiography demonstrating the vasculopathy appeared unilaterally or bilaterally
 
• Competent to give informed consent
 
• Accessible and reliable for follow-up
 

Key Exclusion Criteria
	
 
• Other diseases(such as internal carotid artery stenosis, internal carotid artery dissection, atrial fibrillation, or Intracranial atherosclerosis) probably causing ischemic strokes
 
• Not independent in activity of daily living(The modified Rankin Scale 3-5)
 
• Moyamoya syndrome concomitant with other hereditary or autoimmune diseases(Grave's
 

	
Disease, Type I Diabetes Mellitus, Type I Neurofibromatosis et al)
 
 
• Patient whose initial onset was marked by ischemia but subsequently suffered from intracranial hemorrhage
 
• Emergent evacuation of intracerebral hematoma damaging superficial temporal artery or cortical artery
 
• Emergent decompressive craniotomy causing automatically developed indirect revascularization
 
• Good collateral networks formed by spontaneous anastomosis between extracranial and intracranial vessels before surgery
 
• Life expectancy < 1 years
 
• Pregnancy
 
• Unstable angina or myocardial infarction with recent 6 months
 
• Blood coagulation dysfunction
 
• Allergic to iodine contrast agent
 
• Abnormal liver function (alanine transaminase (ALT) and/or aspartate aminotransferase (AST) > 3 times of normal range)
 
• Serum creatinine > 3 mg/dl
 
• Poorly controlled hypertension (systolic BP > 160 mmHg, diastolic BP > 100 mmHg)
 
• Poor glucose control (fasting blood glucose > 16.7 mmol/l)
 
• Concurrent participation in any other interventional clinical trial
 
• patients refused to participate in the study
 

Sample Size
	
Finally, 100 patients are randomized (1:1) to two groups, 50 of them will undergo direct bypass guided by multimodal neuronavigation, while others will undergo empirical direct bypass procedure.

Follow-up	The face-to-face interview will be performed by study neurologists at 7 days, at discharge, at 3 months, at 6 months and at 12 months (or by telephone) after the recruitment of patients.
------------------	--

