### **6.2. Clinical Secondary Endpoint**

- All kinds of adverse events related to surgery within 30 days
- Infarctions on the contralateral side within 1 year of randomization
- Transient ischemic attack on the surgically treated side within 1 year of randomization

- The changes from baseline in CBF measured by ASL at 7 days, 3 months, 6 months, 12 months or end of trial
- The changes from baseline in modified Rankin Scale (mRS) at 7 days, 3 months, 6 months, 12 months or end of trial
- The changes from baseline in National Institute of Health Stroke Scale (NIHSS) at 7 days, 3 months, 6 months, 12 months end of trial
- The changes from baseline in modified Barthel Scale at 7 days, 3 months, 6 months, 12 months or end of trial

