## **9. Enrollment of Patients**

All of Patients who meet the clinical criteria will undergo MRI, CTP and DSA. Patients with progressive stenosis or occlusion in the terminal portion of the internal carotid artery and/or the initial portion of the anterior or middle cerebral arteries unilaterally or bilaterally and formation of abnormal collateral networks (moyamoya vessels) at the base of the brain according to DSA, hypoperfusion based on perfusion CT or DSA and no significant new infarction lesions on MRI will be asked to participate and sign consent. Once this is completed, the patient will be enrolled and, if randomized to multimodal neuronavigation guiding precise bypass group, will undergo multimodal neuronavigation guiding precise bypass surgery after enrollment.

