## 10. Randomization of Patients

The central randomized method based on our own system. Patient who has signed the informed consent form and met all inclusion criteria without any exclusion item could be enrolled. Once the patient enrolled in the study, the system will automatically assign the study patient a random number with the exact group that he/she should be treated. Then the investigator should record this number and group in the original case history and the coming treatment record of the study patient. According to the protocol, this patient should be treated into the randomized group or the control group.

The investigator's team should archive the randomized list and the related documents (randomized application form) together in the trial folder, which clinical trial department of the site has to store.

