## 12. Multimodal Neuronavigation Procedure

**Pre-procedure:** All patients randomly assigned to both arms will be suspend aspirin 7 days before the revascularization procedure and restart taking aspirin on the first day postoperatively.

**Intra-procedure:** The surgical procedure will be done under the general anesthesia. ICG fluorescence angiography using Flow800 software and electromagnetic neuronavigation system is required during the procedure of revascularization. An

initial ICG fluorescence angiography will be performed when the dural membrane is unfolded to expose the blood vessels on the surface of the brain. According to the appearance order of vessels to assess the velocity of cerebral flow. Neuronavigation system is used to judge the cerebral hypoperfusion area under different recipient vessels. The vessel was chosen as the receptor with lower flow velocity and lower cerebral perfusion area to perform anastomosis.

Papaverine is used to prevent the occurrence of vasospasm. During surgery, the heparinized water was used to flush the donor's and the receptor's lumen for minimization of thrombosis or thromboembolism risk. An anastomotic end-to-side continuous (or intermittent) suture was performed using a 10-0 nonabsorbable vascular suture thread.

**Post-procedure:** Aspirin 100mg per day must be used for the entire duration of follow-up. Clopidogrel is not necessary after the surgery unless a cardiologist recommends taking clopidogrel for a cardiac indication.

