### **13. Antithrombotic therapy**

All participants will take aspirin 100 mg per day for entire follow-up after the revascularization surgery. Suspend aspirin 7 days before surgery, if necessary (Previous vascular stent implantation history), replace the treatment with low molecular weight heparin. If patients have been prescribed long-term use of clopidogrel for indications of coronary disease or peripheral vascular disease, taking clopidogrel at the same time..

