## **16. Schedule of Follow-up and Post-study Follow-up Period**

All patients will be followed up until the primary endpoint or the end of the trial. Complete endpoint information will be obtained with the best effort irrespective of

patient study status, unless patients withdraw consent to participate the trial. Patients will continue to be followed up beyond date of consent withdrawal if they stop the trial and receive other treatment such as medical therapy but agree to provide the prognostic information. The face-to-face interview will be performed by study neurologists at discharge, at 3 months, at 6 months and at 12 months (or by telephone) after the recruitment of patients. If they are more convenient to have access to the study site near to their living areas, patients will be allowed to go to the site for their follow-up.

Visits	Windows	Definition
Randomization	0 day	Study Day 0 day
At discharge	0 day	Based on the number of hospitalization days
At 3 month	7 days	Day 83-97
At 6 months	14 days	Day 166-194
At 12 months	30 days	Day 330-390

Note: 1 month= 30 days

The following procedures will be done at 3 months, at 6 months after enrollment:

- ✧ A neurological evaluation will be performed (Modified Rankin Scale, National Institute of Health Stroke Scale, modified Barthel Scale);
- ✧ A physical examination will be performed, including vital signs (blood pressure, heart rate);
- ✧ Information will be collected on medications, risk factors, and events of interest since the last visit;
- ✧ Computed Tomography Perfusion (CTP), Magnetic Resonance (MR) and Digital subtraction angiography (DSA) will be performed;

The following evaluations will be done at the end of trial:

- ✧ Lab tests for diabetic control and hyperlipidemia management will be performed;
- ✧ A neurological evaluation will be performed (Modified Rankin Scale, National Institute of Health Stroke Scale, modified Barthel Scale);
- ✧ A cognitive function evaluation will be performed (MoCA);
- ✧ Computed Tomography Perfusion (CTP) and Magnetic Resonance (MR) will be done if a patient does not experience a primary endpoint before the end of trial. Images will be transferred to the core imaging evaluation lab.
- ✧ Information will be collected on medications, risk factors, and events of interest since the last visit;

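### The 7-day change-from-baseline assessments are counted from recruitment rather than from surgery, so the 7-day values can be preoperative for some patients and fall on a variable postoperative day for others

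*Protocol*

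**What the plan says.** - **Clock for the 7-day visit.** The follow-up row of Protocol Section 2 (Synopsis) sets the interview "at 7 days, at discharge, at 3 months, at 6 months and at 12 months (or by telephone) after the recruitment of patients".
- **Day 0.** The visit table in Section 16 defines randomization as "Study Day 0 day". Section 10 allocates at enrolment: "Once the patient enrolled in the study, the system will automatically assign the study patient a random number".
- **Surgery.** Section 9 says that a patient allocated to the navigation arm "will undergo multimodal neuronavigation guiding precise bypass surgery after enrollment". It gives no interval and no maximum.
- **Aspirin.** Section 12: "All patients randomly assigned to both arms will be suspend aspirin 7 days before the revascularization procedure". Section 13 repeats the 7 days: "Suspend aspirin 7 days before surgery, if necessary (Previous vascular stent implantation history), replace the treatment with low molecular weight heparin".
- **Endpoints at 7 days.** Section 6.2 lists "The changes from baseline in CBF measured by ASL at 7 days", then at 3, 6 and 12 months or end of trial, with parallel lines for mRS, NIHSS and Barthel. None of these lines names the event from which the 7 days run.
- **Visit lists.** The visit list and window table in Section 16 and the Schedule of Visits in the appendix contain no 7-day visit.

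**The concern.** A change from baseline at 7 days can inform on the choice of recipient vessel only if the operation has taken place. The one sentence that gives the 7 days an origin counts them from recruitment. A patient on aspirin at that point must still pass a 7-day suspension before surgery. If sites follow the text, some 7-day values are recorded before the incision or on the day of it, and others some days after it, all under one label. The comparison between arms at that time point would then be pulled toward no difference. No analysis rule could recover a postoperative value that was never measured.

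**Working it through.** **1. Confirm the clock.** The Section 16 windows reproduce exactly as 30 × months ± window, counted from randomization as Day 0:
- 3 months: 90 ± 7 = Day 83 to 97
- 6 months: 180 ± 14 = Day 166 to 194
- 12 months: 360 ± 30 = Day 330 to 390

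The scheduled visits therefore do run from randomization. Recruitment, enrolment and randomization are treated here as the same day, in line with Section 10.

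**2. Place surgery on that clock.** If surgery is on day D, the 7-day assessment falls on postoperative day 7 − D. If aspirin is stopped on day s, then D is at least s + 7, and the assessment falls on postoperative day 7 − (s + 7) = −s at the latest.

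| Aspirin stopped (day s) | Earliest surgery (day s + 7) | 7-day assessment, latest postoperative day (−s) |
|---|---|---|
| −7 | 0 | 7 |
| −3 | 4 | 3 |
| −1 | 6 | 1 |
| 0 | 7 | 0 (day of surgery) |
| 3 | 10 | −3 (before surgery) |
| 7 | 14 | −7 (before surgery) |

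For any patient still on aspirin at randomization (s ≥ 0), the value is taken on the day of operation or earlier. For a patient who stopped earlier or never took aspirin, the suspension does not force this result. The assessment then falls on day 7 − D, which varies with the unstated D and is again not postoperative if D is 7 or more.

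**3. Look for another origin.** None of the four endpoint lines in Section 6.2 ties its 7 days to surgery. The primary endpoint in Section 6.1 does count its 30 days from surgery, so the protocol uses a surgical origin elsewhere. With no 7-day row in Section 16 and no such column in the Schedule, nothing overrides the synopsis.

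**4. Size.** Four measures at four times give 4 × 4 = 16 comparisons, of which 4 are at 7 days. Suppose a fraction f of patients in each arm has been operated on by the assessment, and the arms do not differ before surgery. The expected 7-day difference is then about f × 1 + (1 − f) × 0 = f of the true early difference: none at f = 0, half at f = 0.5, all at f = 1. The protocol gives no basis for f, so this shows the range and is not an estimate. Even at f = 1 the postoperative day would differ between patients.

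**The case against.** **Not every patient need be affected.** The protocol does not say how many patients take aspirin. Section 3 notes that antiplatelet agents are not used by everyone, although it calls them routine in many operative series. Nothing forbids stopping before consent, and patients are worked up with MRI, CTP and DSA before being asked to join. The Section 12 sentence may say who suspends aspirin, without meaning that suspension begins after allocation. This stands as a limit on extent. A reader might infer that the 7-day comparisons set two wholly untreated groups against each other. The documents do not support that, because some patients may be operated on before Day 7.

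**A postoperative check may have been intended.** The synopsis lists 7 days next to discharge, which is itself not a fixed time from recruitment. That reading is plausible, but it is not what is written.

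**CBF is less certain.** The recruitment clock is stated for an interview, not for imaging. The Schedule labels its post-baseline MRI row as following surgery, starting at discharge, which points to postoperative scans. A reader might infer that the 7-day CBF scan is preoperative by design; the documents do not establish this. They also give the 7-day CBF no other origin.

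**Later visits.** A reader might conclude that all change-from-baseline times should move to a surgical clock. The case is not made for 3, 6 and 12 months, and such a move would conflict with the Section 16 windows.

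**Conclusion.** The point holds in limited form. Followed as written, the synopsis puts the 7-day mRS, NIHSS and Barthel values on or before the day of operation for any patient still on aspirin at randomization, and on a variable day relative to surgery for the rest. For CBF this holds only if the same clock applies. The 7-day changes then mix pre- and postoperative values and are diluted toward no difference.

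The conclusion rests on three things: the recruitment origin is taken literally, the 7-day suspension is observed, and at least some patients are on aspirin at randomization. Section 12 has aspirin restarted after surgery, which presupposes prior use, but no proportion is given. The size of the dilution therefore cannot be worked out from the protocol.

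Four of 16 secondary comparisons are touched. The primary endpoint is not, since its 30 days already run from surgery. The point is worth correcting because the clock decides when patients are examined. It is no reason to doubt the later time points.

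**What to change.** - In the synopsis and Section 6.2, define the 7-day assessment of CBF, mRS, NIHSS and Barthel as 7 days after the date of surgery.
- Add this visit, with a window, to the Section 16 list and table and to the Schedule of Visits, including the ASL scan that the CBF endpoint needs.
- State how randomized patients who are never operated on are handled at this time point. Section 21.2 keeps them in the full analysis set, and they have no surgery date.
- Leave the 3-, 6- and 12-month visits on the randomization clock with their stated windows.

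The cost is wording and one added row or column. The schedule has no 7-day contact to move, but the assessment is already a named endpoint time, so no new endpoint is created. The change concerns assessment timing only and takes no position on the aspirin rule.

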### 3. Study Rationale

#### Epidemiology of MMD

Moyamoya disease (MMD) was originally considered to affect predominantly east Asian populations, has now been observed throughout the world in people of many ethnic backgrounds, including American and European heritage. The distribution of age at onset has been suggested to have two peaks: children who are approximately 5 years of age and adults with a lower peak in their mid-40s. Meanwhile, female patients are nearly twice as male patients. As the most common pediatric cerebrovascular disease in Japan, MMD has a prevalence of 3 cases per 100,000 children. While in Europe the incidence of MMD appears to be only 1/10th of that observed in Japan. Results from a 2005 American review which involved 298 patients with MMD suggests a lower incidence of 0.086 per 100,000. And the incidence rate ratios of specific ethnic origins compared with whites were 4.6 for Asian Americans, 2.2 for African Americans, and 0.5 for Hispanics. Epidemiology studies in mainland China are rare. Miao and co-workers collected data from 202 patients with moyamoya disease in Nanjing between 2000 and 2007 and found the incidence to be 0.43 per 100,000, with female-to-male ratios of 1:1. Furthermore, familial occurrence of MMD has been variably reported: 1.5% or 5.2% in China, and 10%-15% in Japan.

#### Risk of Stroke or Hemorrhage for MMD

The greatest concern for MMD is the risk of subsequent stroke or hemorrhage even with surgical revascularization and regular medical therapy. A retrospective, single-center, cohort study showed most subsequent ischemic events appeared in the first 2 years after surgery. The Kaplan-Meier estimated stroke risk was 10.1% and 12.7% in the first 2 years and 5 years after surgery for all patients treated with surgical revascularization, approximated 10.1% incidence of mortality or TIA or stroke at 1 year after surgery in 802 patients with the MMD. Incidence of rebleeding range from 12.5~20% of patients with onset hemorrhage symptom who underwent revascularization surgery, while with the conservation treatment the rebleeding estimated occurrence of 6.8–65%.

#### Medical Management for MMD

Medical management has been used in patients with MMD, especially when the risk of surgery has been considered to be high or the patient's condition is relatively mild, but there are few data showing either its short-term or long-term efficacy. Antiplatelet agents such as aspirin have been used to prevent emboli from microthrombi formed at sites of arterial stenosis, which may cause ischemic symptoms in patients with MMD, although these agents are not used universally, are used routinely in patients in many

operative series. Anticoagulants such as warfarin are rarely used, although there has been some experience with the use of low-molecular-weight heparin. Calcium-channel blockers can be used to ameliorate intractable headaches or migraines, which are commonly seen in patients with MMD. At the same time, these agents may be also effective in reducing both the frequency and the severity of refractory TIA. However, care must be taken when using them in this patient population due to the role of causing hypotension. Although a large survey from Japan showed no significant differences in outcome between medically and surgically treated patients with MMD. Some recent studies suggest patients with surgical treatment have fewer ischemic events and better life qualities than medical treatment.

